2. STUDY OBJECTIVES AND ENDPOINTS

2.1. Objectives

2.1.1. Primary Objective

- To evaluate the safety, tolerability and immunogenicity of single, ascending SC and IV doses and ascending multiple SC doses of PF-06293620 in subjects with T2DM on stable doses of metformin.

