2.1.3. Exploratory Objectives

- To characterize the pharmacodynamics of PF-06293620.
- To characterize the effect of PF-06293620 on (post-prandial) glucose, insulin, GLP-1, C-peptide and glucagon excursions over 4 hrs following an MMTT.
- To evaluate changes in fasting lipid parameters.
- Additional exploratory objectives in the MAD portion will include 24 hour ambulatory blood pressure monitoring, and central review of ECGs .

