Exclusions Related to Medications

15. Treatment with anti-diabetic therapies other than metformin within 4 weeks of Screening (8 weeks for thiazolidinediones).
16. Change in dietary supplement or herbal medicine within 2 weeks of Screening.
17. Contraindication to metformin therapy, per the metformin label.
18. Known hypersensitivity to metformin.
19. Subject participating in or expecting to participate in other clinical trials.
20. Subjects on chronic systemic corticosteroids [ie, oral, IV or intramuscular (IM)].
21. Treatment with a marketed or investigational monoclonal antibody within 6 months or 5 half-lives (whichever is longer) of Day -1. (Subjects that participated in the SAD portion of the study may participate in the MAD portion of the study with dosing for the MAD starting 6 months after Day 1 in the SAD study [ie, count from day of when single dose administered in SAD] provided they are ADA negative and their last measured glucagon levels during the SAD portion are not above 3X baseline (baseline: pre-dose value prior to dosing in the SAD portion of the study).
22. History of allergic or anaphylactic reaction to any therapeutic or diagnostic monoclonal antibody (IgG protein) or molecules made of components of monoclonal antibodies (eg, Enbrel® which is the Fc portion of an antibody or Lucentis® which is a Fab).
23. History of sensitivity to heparin or heparin-induced thrombocytopenia (if heparin is used to flush intravenous catheters) or known or suspected hypersensitivity to any of the components of drug product.

24. Treatment with an investigational small molecule drug within 90 days or 5 half-lives of Day -1, whichever is longer.

25. Need for radiologic studies involving use of intravascular iodinated contrast materials.

Exclusions for abnormal screening labs or procedures:

Abnormal labs or procedures may be repeated once for confirmation at the discretion of the Investigator (repeat only the abnormal test, not entire panel).

26. FPG <60 or >250 mg/dL.

27. Creatinine clearance \leq 60 mL/min/1.73m² based on the MDRD.

28. Fasting triglycerides >400 mg/dL.

29. Hemoglobin <11 g/dL in females; <12 g/dL in males .

30. Positive anti-drug antibody (ADA) test for PF-06293620, if the subject previously participated in SAD portion (MAD portion of the study only).

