5.4.1. Permitted Medications

Subjects should remain on their dosage of metformin throughout the study. They are allowed to take metformin during the fasting period. As noted in [Section 5.4](#), the date, the time of dose and the dosage must be recorded.

Medications required for treatment of preexisting, stable medical conditions are permitted.

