5.5. Rescue Therapy

Standard medical supportive care must be provided to manage AEs. For medical management of hypoglycemia (See [Section 7.6](#)), the investigator should obtain a blood sample for glucose first and then may administer oral carbohydrate, glucagon or IV glucose according to medical judgment.

For the MAD portion of the study, if a subject has sustained high fasting plasma glucose concentrations on two consecutive measurements (ie, measured on different days), based on the ranges below, the investigator should recommend further follow-up and treatment.

- Fasting Plasma Glucose >270 mg/dL (15 mmol/L) at Week 6.
- Fasting Plasma Glucose >240 mg/dL (13.3 mmol/L) at Week 12.
 - Reinforcement of an appropriate diet is encouraged.

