10.2.2.7. Other Safety Data – Screening and Other Special Purpose Data

The number and percentage of subject receiving study treatment administration will be summarized. The immunogenicity findings, for anti-drug PF-06293620) antibodies (ADA) will be summarized. All concomitant medication(s) as well as non-drug treatment(s) will be provided in the listings.

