10.2.4. Pharmacodynamic Analyses

PD biomarker data will include fasting plasma glucose, fasting glucagon, fasting GLP-1, 24-hr glucose profile (finger-stick), mean daily glucose profile, HbA1c, fructosamine, 1,5-anhydroglucitol, and glucose, insulin, C-peptide, glucagon and GLP-1 AUC after mixed meal tolerance test (MMTT, 4 hr). The relationship between changes in the values of these biomarkers with the pharmacokinetics of PF-06293620 may be explored. Exploratory PK/PD modeling may be performed if visual examination of the data is suggestive of a relationship.

The change and percentage change from baseline for PD biomarkers over the period of the study will be tabulated by treatment. The mean change from baseline values over time per cohort will also be tabulated. Data will be presented in tabular and graphical format and summarized descriptively. Descriptive statistics on change from baseline in fasting plasma glucose, fasting glucagon, fasting GLP-1, 24-hr glucose profile (finger-stick), HbA1c, fructosamine, 1,5-anhydroglucitol, and glucose, insulin, C-peptide, glucagon and GLP-1 AUC after mixed meal tolerance test (MMTT, 4 hr), and lipid parameters will be provided separately for each treatment and the pooled placebo group. The mean change from baseline over time with active treatment may be compared to the mean change from baseline over time with pooled placebo treated subjects using MMRM analysis with treatment as fixed effect, subject as a random effect, and baseline value as covariate adopting unstructured covariance structure. Figures of absolute values, change from baseline, and percentage change from baseline over time may be produced if needed.

The relationship between changes in the values of these biomarkers with the pharmacokinetics of PF-06293620 will be explored. Exploratory PKPD modeling may be performed if visual examination of the data is suggestive of a relationship.

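### The SAP has no rule for MAD glycaemic PD values taken after added glucose-lowering treatment, so by default they enter the comparison with eight pooled placebo subjects

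*Protocol*

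**What the plan says.** The intended background is unchanged metformin. The primary objective is set "in subjects with T2DM on stable doses of metformin", inclusion criterion 3 asks for a stable dose during the study, and Protocol 5.4.1 states: "Subjects should remain on their dosage of metformin throughout the study". Exclusion 15 bars other anti-diabetic drugs in the weeks before Screening. The PD objective is exploratory and reads only: "To characterize the pharmacodynamics of PF-06293620".

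Protocol 5.5 (Rescue Therapy) applies to the MAD part. Its trigger is "sustained high fasting plasma glucose concentrations on two consecutive measurements", on different days, above 270 mg/dL at Week 6 or above 240 mg/dL at Week 12. In that case "the investigator should recommend further follow-up and treatment". No drug or class is named, and the only specific measure is reinforcement of diet. Nothing in 5.5 stops study drug, visits or PD sampling.

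On the analysis side, SAP 10.2.4 states: "The change and percentage change from baseline for PD biomarkers over the period of the study will be tabulated by treatment". It adds that active treatment may be compared with pooled placebo by MMRM. SAP 7.3 uses the Safety Analysis Set for all analyses, and SAP 9 imputes nothing. Concomitant medication is summarised by treatment (SAP 10.2.2) and listed: "All concomitant medication(s) as well as non-drug treatment(s) will be provided in the listings". Neither display is linked to the PD values.

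**The concern.** Rescue is triggered by high glucose, which is also what the glycaemic PD endpoints measure. A value taken after treatment has been added reflects that treatment as well as the assigned arm. If such values are averaged without being marked, late contrasts in fasting glucose, MMTT glucose, mean daily glucose, fructosamine and HbA1c may mix the study drug's effect with the rescue effect.

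Protocol 1.3.1 says that PD in this population should support dose selection in later studies, and SAP section 3 says that the 75 mg cohort was expanded for further PD evaluation. The comparator is small, so one or two subjects could visibly change the picture that informs those decisions.

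**Working it through.** The plan gives no rescue rate, rescue effect or expected PD effect, so there is no figure of its own to reproduce. The two unit conversions in 5.5 agree: 270/18.016 = 15.0 and 240/18.016 = 13.3 mmol/L.

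**Group sizes (SAP Table 2).** Placebo: 2 + 4 + 2 = 8 pooled. Active: 8 (50 mg), 16 (75 mg), 8 (150 mg), 32 in all.

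**Timing (Protocol MAD Schedule of Activities and 6.3).**
- Week 6 is Day 43. Fasting glucose is also drawn on Days 36 and 57, so a confirmed Week 6 trigger falls at about Day 43 or Day 57. It can affect later values, including the Day 64 MMTT and the Day 84–85 mean daily glucose and HbA1c. The Day 8 and Day 28–29 PD data are untouched.
- Week 12 corresponds to Days 84 and 85. Treatment started then comes after the Day 84–85 measurements and can affect essentially only Days 99 to 169.

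**Shift in the contrast.** Let D be the fall in fasting glucose from rescue, k_p the number rescued among the 8 placebo subjects, and k_a the number rescued among n_a in an active group. If the drug lowers glucose, the active-versus-placebo difference moves toward zero by

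D × (k_p/8 − k_a/n_a).

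With D assumed to be 20, 40 or 60 mg/dL:

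| Rescued | D = 20 | D = 40 | D = 60 | Direction |
|---|---|---|---|---|
| 1 placebo, 0 active | 2.5 | 5.0 | 7.5 | toward zero |
| 2 placebo, 0 active | 5.0 | 10.0 | 15.0 | toward zero |
| 1 placebo, 1 of 16 active | 1.25 | 2.5 | 3.75 | toward zero |
| 1 placebo, 1 of 8 active | 0 | 0 | 0 | none |
| 0 placebo, 1 of 8 active | −2.5 | −5.0 | −7.5 | away from zero |

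If the true on-treatment difference were 40 mg/dL (an assumption), one rescued placebo subject and no rescued active subject would shrink it by 6%, 12.5% or 19%. Two would shrink it by 12.5%, 25% or 37.5%.

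**How often.** A simulation of placebo subjects assumed mean fasting glucose 160–200 mg/dL, between-subject SD 40, within-subject SD 20, upward drift 0–30, and entry limited to 60–250 mg/dL (exclusion 26).
- Week 6 trigger: 0.05% to 4.7% of placebo subjects, so a 0.4% to 32% chance of at least one in 8.
- Week 12 trigger: 0.9% to 22%, so a 7% to 87% chance of at least one in 8.

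The average Week 6 shift in the placebo mean is D × rate. With D = 40 it runs from 40 × 0.0005 = 0.02 to 40 × 0.047 = 1.9 mg/dL.

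**The case against.** The strongest reply is that the SAP has no rule to keep these values. That is right: they stay in through silence. SAP 7.8.2 also lets significant protocol deviations be reviewed before database closure. However, treatment recommended under 5.5 follows the protocol and is not clearly a deviation. The deviation definitions in Appendix 3 are still to be written, and the sponsor team is unblinded (Protocol 5.2), so an exclusion chosen late would be hard to defend.

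A reader might infer that placebo is necessarily pulled toward active. The documents do not establish this. More rescue on placebo is plausible if the drug works, but there are 32 active subjects, and balanced or active-heavy rescue gives no shift or the opposite one.

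A reader might also note that entry is allowed up to 250 mg/dL, so a subject at 241–250 with no change already exceeds the Week 12 limit, and conclude that end-of-treatment results are contaminated. They are not, because that trigger comes too late to affect them. On-treatment values are exposed only through sustained readings above 270 mg/dL at Week 6, which is above the entry ceiling and should be uncommon. Nor should a constant 40 mg/dL effect be carried into follow-up. With the half-life of 9 to 18 days in Protocol 1.3.2, Day 99 is 42/18 = 2.3 to 42/9 = 4.7 half-lives after the Day 57 dose.

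Two further replies stand in part. Including all values is a legitimate choice of question. And in a study this small, rescued subjects can be found in the listings, although a reader of the summary tables would not see them.

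**Conclusion.** The gap is real and modest. As written, MAD PD values after added glucose-lowering treatment enter the summaries and any MMRM unmarked. Each rescued placebo subject shifts the pooled placebo mean by one eighth of the rescue effect, or 2.5–7.5 mg/dL if that effect is 20–60 mg/dL. Direction depends on where rescue falls, and with no rescue there is no distortion. The rescue rate, its effect and the true drug effect are all assumptions.

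A reader might conclude that the primary objective is compromised. It is not: that objective concerns safety, tolerability and immunogenicity. The PD comparison is exploratory, the MMRM is optional, and no hypothesis test or power statement is involved. The case for a change rests on its low cost and on the small comparator.

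**What to change.** In SAP 10.2.4, for the MAD glycaemic PD endpoints and before database lock:

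- Flag every value collected after the start of any glucose-lowering drug other than metformin, or after a metformin dose increase. Protocol 5.4 and 5.4.1 already have the dates and doses recorded.
- Report the number of subjects with such treatment, and its timing, by arm.
- Present the descriptive tables, and the MMRM if it is run, both including and excluding the flagged values. State that the exclusion analysis assumes missing at random, a real limitation with 8 placebo subjects.
- Keep all data for safety.

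The cost is a programming flag, one extra set of tables, and fewer late placebo values in the exclusion analysis. No rescue threshold or treatment is changed.

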6. STUDY PROCEDURES

6.1. Screening

Subjects will be screened within 28 days prior to administration of the study medication for the SAD cohorts and 42 days prior to administration of the study medication for the MAD cohorts to confirm that they meet the subject selection criteria for the study. The investigator

(or an appropriate delegate at the investigator site) will obtain informed consent from each subject in accordance with the procedures described in [Section 12.3](#) on Subject Information and Consent. If the time between Screening and dosing exceeds 28 days for the SAD cohorts or 42 days for the MAD cohort as a result of unexpected delays (eg, delayed drug shipment) or current cohort enrollment complete (eg, subject eligible but to be considered in future cohort) then subjects do not require re-screening if the eligibility laboratory assessments are repeated prior to randomization – and the results meet the eligibility criteria. Also, a subject who qualified for this protocol but did not enroll from an earlier cohort may be used in a subsequent cohort without re-screening provided the eligibility laboratory assessments are repeated prior to randomization and laboratory results meet the eligibility criteria for this study. If a subject fails to meet eligibility due to a laboratory test, the test may be repeated once within the 28 days (SAD Cohorts)/42 days (MAD Cohorts) prior to administration of the study medication, at the Investigator's discretion, in an effort to confirm eligibility.

The following procedures will be completed for subjects screening for the SAD and MAD portion, unless otherwise noted:

- Obtain written informed consent.
- Review Inclusion and Exclusion criteria.
- Collect demographic information (age, gender, ethnicity, etc)
- Obtain medical history, including history of recreational drug, alcohol and tobacco use.
- Obtain complete medication history of all prescription or nonprescription drugs, and dietary and herbal supplements taken within 28 days prior to the planned first dose.
- Conduct full physical examination including height and weight (See [Section 7.2](#) for height and weight instructions).
- Confirm subject is using appropriate contraception methods per [Sections 4.4.3.2](#) and [4.4.3.3](#).
- Obtain temperature and supine vital signs.
- Collect standard supine 12-lead electrocardiogram (ECG).
- Collect urinalysis (clean catch, midstream) and urine drug test (illicit drugs).
- Following at least 10-hr fast, collect blood specimens for the following:
 - Safety laboratory tests [hematology, chemistry];
 - Screening labs (TSH, C-peptide, HIV, hepatitis B surface antigen, hepatitis B core antibody, hepatitis C antibody);

- Serum FSH concentration (women only);
- Fasting lipid profile;
- Creatine kinase (performed in MAD cohorts only as part of MAD routine serum chemistry);
- Apo B (MAD only);
- Coagulation panel, amylase and lipase;
- HbA1c;
- Fasting plasma glucose (FPG);
- ADA (collected only from subjects who participated in the SAD portion, and are undergoing screening for the MAD portion).

To prepare for study participation, subjects will be instructed on the use of the [Lifestyle Guidelines](#) and [Concomitant Medication\(s\)](#) sections of the protocol.

6.2. Study Period – SAD Cohorts

For the study period described below, when multiple procedures are scheduled at the same time point(s) relative to dosing, the following chronology of events should be adhered to, where possible.

- ECGs: obtain prior to vital signs and as close as possible to scheduled time, but prior to blood specimen collection;
- Blood pressure/pulse rate: obtain as close as possible to scheduled time, but prior to blood specimen collection;
- Pharmacokinetic blood specimens: obtain at scheduled time within 10% of the nominal time from dosing;
- Other procedures: obtain all other procedures as close as possible to the scheduled time, but may be obtained before or after blood specimen collection.

6.2.1. Day -2 (SAD)

Subjects will be admitted to the Clinical Research Unit. Subjects will be required to stay in the Clinical Research Unit for 6 nights and will be discharged on Day 5.

Site staff will review concomitant medications, adverse events and contraception method. Concomitant medications will be recorded in medication history. Any noted adverse events will be recorded as prior medical history.

On admittance to the CRU, subjects will undergo a urine drug screen (for illicit drugs).

6.2.2. Day-1 - SAD

On Day -1, after an overnight fast of at least 10 hours, and the following procedures will be completed:

- Review medical history including recreational drug, alcohol and tobacco use, and medication history.
- Conduct limited physical exam of the skin, heart, lungs, abdomen and extremities by trained medical personnel at the investigator site.
- Collect fasting weight and triplicate waist circumference.
 - To measure waist circumference, use a spring-loaded tape measure, and starting at the top of the hip bone, bring it all the way around, level with the navel. Tape measure should not be too tight and parallel with the floor. Instruct subject to not hold their breath. Measurement should not include navel.
- Obtain temperature and supine pulse and supine triplicate blood pressure. Blood pressure will be the only vital sign collected in triplicate.
- Collect blood samples for the following:
 - Fasting lipid profile;
 - HbA1c;
 - Fructosamine;
 - 1,5-anhydroglucitol;
 - ADA;
 - Banked Specimen (Pharmacogenomics).
- Collect adverse events.
- Question subjects regarding metformin compliance.
- Obtain fingerstick glucose before breakfast (before MMTT).
- Before MMTT, collect 0 minute fasting timepoint blood samples for FPG, C-peptide, insulin, glucagon and GLP-1 (all cohorts).

- Administer MMTT in AM; begin sample collection (glucose, C-peptide, insulin, glucagon and GLP-1):
 - 15 minutes from start of meal (first sample collected 5 minutes post meal; the liquid should take 10 minutes to consume; See [Section 7.4.1.2](#));
 - 30 minutes;
 - 60 minutes;
 - 120 minutes;
 - 180 minutes;
 - 240 minutes.
- Obtain fingerstick glucose measurements 2 hr post- breakfast, before lunch, 2-hr post-lunch, before dinner, 2-hr post-dinner, prior to snack (between 9 and 10 PM).
- Initiate continuous cardiac telemetry at least 12 hours prior to dosing on Day 1.
- Randomize subject to study treatment.

6.2.3. Day 1 - SAD

Prior to dosing, the following procedures will be completed:

- Obtain finger-stick glucose measurement at 0300 and prior to breakfast.
- Obtain fasting weight.
- Collect a blood sample for pharmacokinetic analysis.
- Collect blood samples for the following:
 - Hematology;
 - Fasting clinical chemistry;
 - Coagulation panel, amylase and lipase.
- Collect blood for FPG, fasting glucagon and fasting GLP-1 (SAD SC Cohorts 1-4).
- **For SAD IV Cohort 5 only**, collect the time 0 minute fasting blood samples for FPG, C-peptide, insulin, glucagon and GLP-1 (prior to MMTT).
- Collect urine for Urinalysis (clean catch, midstream).

- Collect triplicate 12-Lead ECG.
- Collect temperature and supine pulse and supine triplicate blood pressure. Blood pressure is the only vital sign to be collected in triplicate.
- Maintain continuous cardiac telemetry.
- Assess symptoms by spontaneous reporting of adverse events and by asking the subjects to respond to a non-leading question such as "How do you feel?"
- Administer the study medication (see [Study Treatments](#) and [Administration](#) Sections).

After dosing, the following procedures will be completed:

- Assess temperature, supine pulse rate and supine triplicate blood pressure at 1, 2, 4, 8 and 12 hours after dosing. Blood pressure is the only vital sign to be collected in triplicate.
- Obtain triplicate 12-lead ECG measurements at 1, 2, 4, 8 and 12 hours after dosing.
- Collect blood samples for pharmacokinetic analysis at 1, 4, 8 and 12 hours following dosing on Day 1.
- Maintain continuous cardiac telemetry following dose administration.
- Injection site assessment:
 - SC administration: immediately after injection, 15 and 30 minutes, 1, and 2 hours post administration. Additional assessments should be performed as needed after the last assessment of 2 hrs post-dose on dosing days.
- Infusion reaction assessment during and immediately after infusion:
 - IV administration: 15 and 30 minutes, 1 and 2 hours post administration.
- Record concomitant medication.
- Assess symptoms by spontaneous reporting of adverse events and by asking the subjects to respond to a non-leading question such as "How do you feel?"
 - IV administration only (**SAD Cohort 5 only**): Administer MMTT (within approximately 15 minutes) at the end of the IV infusion and collect samples (glucose, insulin, C-peptide, glucagon and GLP-1) at:
 - 15 minutes (5 minutes after fluid meal is consumed which requires 10 minutes, See [Section 7.4.1.2](#));

- 30 minutes;
- 60 minutes;
- 120 minutes;
- 180 minutes;
- 240 minutes.
- Obtain fingerstick glucose (2-hr post breakfast, before lunch, 2-hr post-lunch, before dinner, 2-hr post-dinner, prior to snack (between 9 and 10 pm).

6.2.4. Day 2 – SAD

The following procedures will be completed:

- Obtain fingerstick glucose at 0300 and before breakfast.
- Assess injection site for reactions if necessary (required if reaction was noted on Day 1).
- Collect blood samples for pharmacokinetic analysis at 24 and 36 hours after Day 1 dosing.
- Collect blood samples for FPG and fasting glucagon.
- Collect fasting blood and urine samples for safety laboratory tests 24 hours after Day 1 dosing (hematology, chemistry, urinalysis (clean catch, midstream)).
- Assess temperature, supine pulse and triplicate supine blood pressure 24 hours after Day 1 dosing. Blood pressure is the only vital sign to be collected in triplicate.
- Obtain triplicate 12-lead ECG measurements 24 hours after Day 1 dosing.
- Discontinue continuous cardiac telemetry in AM before breakfast.
- Assess symptoms by spontaneous reporting of adverse events and by asking the subjects to respond to a non-leading question such as “How do you feel?”
- Record concomitant medications.

